### 16.6. HANDLING OF MISSING DATA

The primary statistical analysis will be conducted using the observed data with standard imputations used when the 12 month DUS determination is missing but an earlier or later DUS

or angiogram are available in the ITT sample (see Primary Statistical Analysis in **Section 16.8** for more detail).

Additionally, a sensitivity analysis to the missing data in the intent-to-treat sample will be conducted. The sensitivity analysis will include a best case, worst case and tipping point analysis. The best case analysis will impute successes for the missing data. The worst case analysis will impute failures for missing data. The tipping point analysis starts with the best case analysis and continues until the worst case analysis is completed, by increasing the number of missing cases imputed as failures by one in each analysis. The goal of the tipping point analysis is to determine at what point the imputation of failures causes the statistical evaluation of the endpoint to lose statistical significance. If the worst case analysis maintains statistical significance, the tipping point analysis is not necessary.

#### 16.7. SUMMARY OF BASELINE DEMOGRAPHICS, INDEX PROCEDURE MEASUREMENTS, TACK ENDOVASCULAR SYSTEM TREATMENT RESULTS, AND SUBJECT COMPLIANCE

Baseline demographics including at a minimum, gender, age and selected medical history will be summarized for patients enrolled in the study. In addition, angiographic characteristics and measurements, as well as final treatment results captured during each phase of the Index Procedure (Baseline, Post-PTA, and Post-Study Device) as outlined in **Section 10** will also be summarized.

Patient follow-up and compliance with the protocol will be reported. The number and percent of patients enrolled, completing study required follow-ups and completing the study will be summarized. The patients who exit the study early will be summarized along with the reason for early study termination.

#### 16.8. PRIMARY SAFETY OBJECTIVE

Subjects Included the Analysis: Subjects who meet the ITT definition as specified in **Section 16.2 and 10.3.1**.

Endpoint: Freedom from the occurrence of any new-onset major adverse event(s) (MAEs) defined as index limb amputation (above the ankle), CEC adjudicated clinically-driven target lesion revascularization (CD-TLR), or all-cause death at 30 days as specified in **Section 6.1**.

Hypothesis and Performance Goal: The VIVA performance goal of 88% will be used as the performance goal for this endpoint.

H0: Freedom from MAE (pMAE) is less than or equal to 88% at 30 days, pMAE ≤ 88%

H1: Freedom from MAE is greater than 88% at 30 days, pMAE > 88%

Sample Size Rationale: Using PASS 2012, a one-sample Exact Test, power = 90%, one-sided Type I error controlled at 5.0%, a performance goal of 88% and an assumed freedom from MAE at 30 days in Group 1 of 95%, 138 subjects with 30 days of follow-up and/or an MAE prior to 30 days are required for the analysis.

---

**Primary Statistical Analysis:** The primary statistical analysis will be conducted in subjects who meet the ITT definition and have observed data for the primary safety endpoint. The primary statistical method is a one-sample exact test comparing the proportion of subjects free from a MAE to the performance goal using a one-sided  $\alpha = 0.05$ . The exact one-sided 95% confidence interval for the proportion of subjects free from MAE will be calculated.

The freedom from MAE proportion will be calculated such that the numerator is the number of subjects in whom a MAE did not occur within 30 days of the index procedure. The denominator is the number of subjects with 30 days of follow-up plus the number of subjects with an MAE prior to 30 days who exited the study early, if any.

**Additional Analysis:** If pooling is not justified per the methods outlined in **Section 16.5**, the additional analyses specified in that section will be completed. If there is missing data for the ITT subjects, the sensitivity to missing data analysis outlined in **Section 16.6** will be completed. Additionally, the primary statistical analysis will be conducted in the per protocol sample.

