#### 12.9. FOLLOW-UP VISIT COMPLIANCE

As part of the informed consent process, all reasonable efforts will be made to obtain complete data for all subjects according to the follow-up visit schedule. Investigators and research staff will be expected to maintain continuous and open communication with study subjects regarding their participation in this study.

Three attempts via telephone will be made to contact subjects who do not present for study follow-up visits. If after three telephone attempts, the subjects cannot be contacted, a certified letter should be sent by the PI or designated study coordinator to the subject’s last known address. If possible, public records should be searched to ascertain survival status. If efforts to reach the subject are unsuccessful after three telephone contacts and a certified letter and there is no evidence of subject expiration, the sites will complete a Protocol Deviation for a Visit Not Done. A detailed record of all contact attempts should be maintained in the subject’s file. This process should be repeated for every subsequent follow-up visit and documented accordingly. These subjects will not be considered lost-to-follow-up (LTFU) and exited from the study until the end of the final follow-up visit window, unless it becomes known to the site that the subject has expired or wishes to withdraw consent.

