#### 12.10. SUBJECT DISCONTINUATION AND REPLACEMENT

A subject may discontinue participation at any time without penalty or loss of benefits to which the subject is otherwise entitled. In addition, a subject may be discontinued if in the investigator’s opinion it is in the subject’s best interest. If a subject prematurely discontinues from the study, the reason will be recorded in the eCRF with supporting documentation. These results will be tabulated by number and percent for each category for discontinuation.

Subjects who prematurely exit the study after treatment will have their data maintained and evaluated up until the time of withdrawal. Subjects who are voluntarily or involuntarily (per PI discretion) withdrawn cannot re-enter the study. These subjects will not be replaced.

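### The safety denominator in 16.8 counts an MAE without 30 days of follow-up only after an early exit, so a known non-fatal MAE in a subject never contacted again drops out

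*Combined protocol and SAP*

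**What the plan says.** Section 16.8 describes the safety analysis set in three places.

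- **Sample Size Rationale:** "138 subjects with 30 days of follow-up and/or an MAE prior to 30 days are required for the analysis". Exit status plays no part.
- **Primary Statistical Analysis, opening sentence:** ITT subjects who have observed data for the endpoint. The term is not defined.
- **Primary Statistical Analysis, counting rule:** "the numerator is the number of subjects in whom a MAE did not occur within 30 days of the index procedure". The denominator is the subjects with 30 days of follow-up, "plus the number of subjects with an MAE prior to 30 days who exited the study early, if any".

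Section 12.9 deals with subjects who cannot be reached by telephone or certified letter: "These subjects will not be considered lost-to-follow-up (LTFU) and exited from the study until the end of the final follow-up visit window". Its exceptions are a death that becomes known to the site and a wish to withdraw consent.

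Table 5 and Section 12.1 open the 30-day visit window two days early, so a valid visit can fall on day 28 or 29. Section 16.8 does not say whether such a visit supplies 30 days of follow-up.

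**The concern.** The sample-size sentence and the counting rule disagree about one kind of subject: an MAE before day 30, no later contact and no formal exit. The first includes that subject and the second does not. Section 12.9 makes the gap reachable, because going silent is not an exit.

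The subject lost this way is a recorded safety failure, a CD-TLR or an index-limb amputation. Removing a failure can only raise the MAE-free proportion. This is the decision statistic for one of the two primary endpoints, so the rule should give one answer for every subject. If the case were coded as missing instead, the best-case analysis in Section 16.6 would score a known failure as a success.

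**Working it through.** **Inputs, all from Section 16.8:** performance goal 88%; assumed rate 95%; one-sample exact test; one-sided alpha 0.05; power 90%; 138 subjects required.

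**Step 1. Reproduce the plan's figure.** The pass mark r is the smallest count with P(X ≥ r | n, 0.88) ≤ 0.05. The required n is the smallest with P(X ≥ r | n, 0.95) ≥ 0.90. The first such n is 138, with r = 128, exact alpha 0.0493 and power 0.914. The plan's 138 is confirmed.

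**Step 2. Sort the subjects under the two texts of 16.8, with 12.9.**

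| Subject | Sample-size sentence | Counting rule |
|---|---|---|
| MAE before day 30, seen later | in | in (has 30 days of follow-up) |
| MAE before day 30, then withdrew consent | in | in (early exit) |
| Known death before day 30 | in | in, if recorded as an exit |
| Non-fatal MAE before day 30, never reached again | in | **out** |
| MAE-free, followed to day 30 | in | in |
| MAE-free, withdrew before day 30 | out | out of the denominator |

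Only the fourth row differs.

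**Step 3. Effect on the test.** The p-value is P(X ≥ s | n, 0.88) for s successes in n subjects. The MAE counts and the number of silent MAE subjects are assumptions.

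| Evaluable, MAEs | Silent MAEs dropped | Result | Pass mark | p | Outcome |
|---|---|---|---|---|---|
| 206, 17 | 0 | 189/206 | 190 | 0.056 | fail |
| 206, 17 | 1 | 189/205 | 189 | 0.035 | pass |
| 210, 18 | 0 | 192/210 | 193 | 0.073 | fail |
| 210, 18 | 1 | 192/209 | 192 | 0.048 | pass |

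**Step 4. How often the result lies there.** The probability of exactly 17 MAEs in 206 is 1.5% if the true MAE-free rate is 95%, and 2.2% if it is 88%. That is before requiring one of the 17 to be silent. At 95% the expected number is 206 × 0.05 = 10.3 MAEs, and power at 206 is 97%.

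**Step 5. The other reading of 30 days of follow-up.** Suppose it means still being on study at day 30. Section 12.9 keeps silent subjects on study, so the silent MAE is counted. But a silent subject with no recorded event then also enters the denominator, and as a success. With 17 MAEs and 2 such subjects among 210, the result is 193/210, p = 0.0456 (pass). Leaving the 2 out as unknown gives 191/208, p = 0.0503 (fail). This reading closes one gap and opens another.

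**The case against.** The best defence is that the intended set appears in the same section. The sample-size sentence includes every early MAE, and a careful analyst would follow it. The exposed case is also narrow: the MAE must be known and non-fatal, the subject must not withdraw, and nobody may ever see the subject again. Deaths known to the site fall under the exception in 12.9, and any later visit supplies the follow-up. Section 16.6 adds worst-case and tipping-point analyses, and the examples above sit at the pass boundary by construction.

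All of that stands as a limit on size. It does not remove the conflict, because the counting rule is the operative text and adds an exit condition that the sample-size sentence lacks. The efficacy denominator in Section 16.9 has no such condition: it counts any clinically driven TLR before the 12-month window closes. The analyses in 16.6 are sensitivity analyses and do not define the primary statistic.

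A reader might go further and infer that subjects who leave early without an event count as successes, since the numerator sentence carries no follow-up condition and Section 12.10 says that early exits "will have their data maintained and evaluated up until the time of withdrawal". Adding such subjects to the numerator alone would inflate the false-pass rate. The documents do not support that reading. The preceding sentence limits the analysis to subjects with observed endpoint data. An exact test needs successes that are a subset of n: with 210 enrolled, 10 MAEs and 12 event-free early exits, the numerator-only count is (210 − 10)/(210 − 12) = 200/198, or 101%, which cannot be tested. Section 12.10 limits use of the data to the time observed; it does not make a withdrawal on day 10 MAE-free at day 30.

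**Conclusion.** The point holds in a narrow form and is minor. As written, the denominator in 16.8 conflicts with the section's own sample-size sentence and, read with 12.9, omits a known non-fatal MAE in a subject never contacted again. The error can only favour the device. It should affect 0 or 1 subject and would change the decision only when the result lies at the pass mark. The 0-to-1 figure is an assumption, because the documents give 15% attrition over 12 months and no 30-day loss rate.

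Nothing here shows that the sample size, test, goal or alpha is wrong. Saying that the numerator is a subset of the denominator is a clarification only.

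**What to change.** Replace the two counting sentences in Section 16.8 with:

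> Denominator: ITT subjects with an MAE on or before day 30, whatever their later follow-up or exit status, plus ITT subjects known to be MAE-free through day 30 (or through a 30-day visit held on day 28 or 29). Numerator: members of this denominator without an MAE on or before day 30.

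MAE-free subjects lost before then remain missing and go to the analyses in 16.6, as the plan already intends. The wording agrees with the sample-size sentence and settles the day-28 and day-29 visits. The cost is one change of text. The required 138 is unchanged, and so is the method for setting the pass mark. The reported proportion may be slightly less favourable if such a subject occurs.

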#### 16.9. PRIMARY EFFICACY OBJECTIVE

**Subjects Included the Analysis:** Subjects who meet the ITT definition as specified in **Section 16.2** and **10.3.1**.

**Endpoint:** Primary patency defined as freedom from CEC adjudicated clinically-driven target lesion revascularization (CD-TLR) and freedom from core lab adjudicated duplex ultrasound derived binary restenosis at 12 months (defined as PSVR  $\geq 2.5$ ) as specified in **Section 6.1**.

**Hypothesis:**

H0: Primary patency ( $p_{p\_pat}$ ) is less than or equal to performance goal (PG) at 12 months,  $p_{p\_pat} \leq PG$

H1: Primary patency is greater than the performance goal at 12 months,  $p_{p\_pat} > PG$

**Performance Goal:** The performance goal is based upon the 12 month primary patency results from the recently completed Levant 2 IDE trial that supported approval of the test DCB. The Levant 2 randomized controlled trial used the same primary efficacy endpoint as the TOBA II trial and represents current estimates for primary patency associated with PTA using standard and drug-coated balloons. The primary patency estimates for the ITT completer population from Levant 2 are provided in **Table 7**.

**Table 7 - Primary Patency at 1 Year in LEVANT 2 for ITT Completers**

Measure	Test Drug-Coated Balloon (DCB) %(n/N) [95% CI]	Control PTA %(n/N) [95% CI]
Primary Patency	65.2% (172/264) [59.4, 70.9]	52.6% (71/135) [44.2, 61.0]

The performance goal for TOBA II is derived from the lower limit of the 95% confidence interval for the Test DCB and Control PTA in Levant 2 given that the expectation is that the Tack

device will resolve dissections without negatively impacting primary patency at 12 months. The primary patency rate is dependent on the type of balloon used and therefore the performance goal will be calculated using the Levant 2 lower 95% confidence limits and the proportion of subjects enrolled and treated with DCB ( $p_{DCB}$ ) and Control PTA ( $p_{PTA}$ ) in the TOBA II Trial. The following formula will be used:

$$PG = p_{DCB} \times 59\% + p_{PTA} \times 44\%$$

For example, assuming the proportion of subjects meeting the ITT definition in TOBA II is 60% DCB and 40% Control PTA, the calculated performance goal will be  $0.6 \times 59\% + 0.4 \times 44\% = 53\%$ . The primary efficacy performance goal will be calculated upon completion of the index procedure for all enrolled subjects (see **Section 16.4**).

*Sample Size Rationale:* The sample size required to have data evaluable for the primary efficacy endpoint at 12 months, was calculated using PASS 2012, a one-sample Exact Test, power = 90%, one-sided Type I error controlled at 2.5%, and setting the maximum proportion of subjects treated with DCB enrolled at 60%. In this case, the performance goal for primary patency at 12 month is 53%. A current estimate for primary patency at 12 months in the TOBA European trial (POBA use only) is 75%. Conservatively, the primary patency for DCB + Tack and Control PTA + Tack was assumed to be 65% for the purpose of the sample size calculation. Using those assumptions, 178 subjects are required to have data evaluable for the primary efficacy endpoint at 12 months.

The power at N=178 subjects is provided in **Table 8** varying the assumed proportion of subjects treated with DCB + Tack. As can be seen in **Table 8**, the sample size calculation for the TOBA II trial has at least 90% power given the proportion of subjects treated with DCB + Tack is 60% or less.

**Table 8 - Power for N=178 Subjects Varying the Proportion of Subjects Treated with DCB + Tack Meeting the ITT Definition with Data Available to Evaluate the Primary Efficacy Endpoint at 12 months**

Proportion of Subjects Meeting ITT Definition with Tack +		Performance Goal a	Assumed Patency at 12M for TOBA II			Power at N=178
DCB	Control PTA		DCB + Tack	Control PTA + Tack	Pooled	
30%	70%	49%	65%	65%	65%	99.1%
40%	60%	50%				98.0%
50%	50%	52%				92.4%
60%	40%	53%				90.0%

aThe performance goal, PG, is calculated as PG = proportion DCB + Tack\*59 + proportion control PTA + Tack\*44.

*Primary Statistical Analysis:* The primary statistical analysis will be conducted in subjects who meet the ITT definition and have data evaluable for the primary efficacy endpoint. Subjects with a missing DUS ultrasound at 12 months and a patent DUS ultrasound at a later visit with no intervening clinically driven TLR will be considered patent at 12 months. In the event an angiogram is available within the 12 month visit window, the angiographic core-lab determined stenosis using the 50% cutoff will be used instead of the DUS core-lab determined stenosis. The primary statistical method is a one-sample exact test comparing the proportion of subjects with

primary patency to the performance goal using a one-sided  $\alpha = 0.025$ . The exact two-sided 95% confidence interval for the proportion of subjects with primary patency will be calculated.

The primary patency proportion will be calculated such that the numerator is the number of subjects who are patent at 12 months with no clinically-driven TLR by the close of the 12 month visit window. The denominator is the total number of subjects with a core-lab adjudicated DUS ultrasound finding of either patent or not patent at 12 months, clinically-driven TLR prior to the close of the 12 month visit window, or missing 12 month DUS with a patent DUS finding at a subsequent visit with no intervening clinically driven TLR.

*Additional Analysis:* If pooling is not justified per the methods outlined in **Section 16.5**, the additional analyses specified in that section will be completed. If there is missing data for the ITT subjects, the sensitivity to missing data analysis outlined in **Section 16.6** will be completed. Additionally, the primary statistical analysis will be conducted in the per protocol sample.

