#### **Table 5. Time and Events Schedule**

Assessment	Baseline 	Implant Procedure	Pre-Discharge	30-day (-2 days/+14 Days)	6 Month (±30 Days)	12 Month (± 30 Days)	24 Month (± 30 Days)	36 Month (± 30 Days)	Unscheduled 
Informed Consent	X 								
Medical History / Physical Exam	X								
Serum Creatinine	X								
PT/ INR 	X								
Urine pregnancy test if female 	X								
Ankle Brachial Index (ABI)	X		X 	X	X	X	X	X	X
Rutherford Classification	X			X	X	X	X	X	X
Pre-procedural Medications		X							
Angiogram		X							X 
Study Medications		X	X	X	X	X	X	X	X
Duplex Ultrasound (DUS) 				X	X	X			X 
X-ray of Implanted Tacks 						X 			X 
Adverse Event Assessment		X	X	X	X	X	X	X	X
Peripheral Artery Questionnaire (PAQ)	X			X	X	X	X	X	X
EQ-5D-3L	X			X	X	X	X	X	X
Walking Impairment Questionnaire (WIQ)	X			X	X	X	X	X	X

 Assessments may be done up to 30 days before the procedure, with the exception of a pregnancy test

 Consent to be obtained within 30 days prior to enrollment.

 PT/INR to be obtained only if subject is on chronic warfarin therapy.

 Negative urine pregnancy test within 7 days of the Index Procedure is required for women of childbearing potential.

 All scheduled DUS exams should be performed per the protocol established by the core lab. If a DUS is non-diagnostic (per the imaging protocol), the site should make every effort to obtain a repeat exam within the visit window.

 Assessment of Tack Integrity. All required and unscheduled X-ray exams should be performed in accordance with the core lab protocol.

 Unscheduled visit data should be captured for a target limb related adverse event or intervention to target limb. If intervention to the target limb occurs, the data for assessments performed prior to the interventional procedure should be recorded in the eCRF.

 Only required for subjects in whom at least one Tack was placed during the index procedure.

 If clinically indicated or per standard of care.

 Pre-discharge ABI may be assessed up to 72 hours post-index procedure.

NOTE: All imaging of the target limb acquired during scheduled and unscheduled visits (such as Angiogram, DUS or X-Ray) should be submitted to the respective core lab within 3 days of occurrence.

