#### 12.6. REVIEW OF CONCOMITANT MEDICATIONS (ANTIPLATELETS/ANTICOAGULANTS) DUPLEX ULTRASOUND (DUS) ASSESSMENT

Lower extremity arterial duplex ultrasonography is widely accepted as a method of determining arterial stenosis. Duplex ultrasonography combines spectral Doppler Technology in addition to B-mode imaging to allow the visualization of blood flow patterns within the arteries and veins. This spectral Doppler also provides a method to measure the velocity of the blood flow at specific locations.

The peak systolic blood flow velocity within the Tacks as well as the target vessel will be taken to determine the peak systolic velocity ratio (PSVR). All scheduled and unscheduled DUS exams shall be reviewed by an independent core laboratory for analysis.

The DUS exam should be performed on all subjects at the 30-day, 6, and 12 month follow-up visits. Duplex ultrasonography and/or angiography should be performed prior to any endovascular intervention during the follow-up period in order to assess the treated vessel patency. Operators should have experience with DUS and the specific methods for calculating the blood flow velocities. Operators will be trained on the DUS protocol provided by the respective core laboratory. Each operator is required to submit a test case DUS exam to the core lab prior to performing any study-required DUS exams.

A comprehensive overview for DUS acquisition requirements can be found in the core laboratory manual.

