#### 12.8. UNSCHEDULED VISITS

A subject who presents to the investigational site between scheduled study-required follow-up visits for a target limb related adverse event or intervention to target limb is considered to have an “unscheduled visit”. Every effort should be made to gather data from the same clinical assessments required at the 12 month follow-up visit, including angiographic (if Target limb revascularization occurs), DUS and X-ray imaging (if clinically indicated or per standard of care). At the very least, target limb resting ABI measurement and Rutherford Classification should be assessed prior to any intervention to the target limb. In any case, if a Target limb intervention occurs, all the data from any assessment (clinical or imaging) performed prior to the intervention should be recorded in the Unscheduled Visit eCRF.

In the event a subject receives an intervention on the target vessel and/or lesion, all associated media (angiographic, DUS and X-Ray) shall be performed in accordance with imaging protocols and should be provided to the respective core labs. If a subject presents for target limb intervention that does not involve the target vessel/lesion, but the imaging performed captures the target lesion and Tacked portion vessel, such imaging should be sent to the respective core lab.

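### After a missed 12-month duplex scan, a later scan counts in the primary patency analysis only if it is patent; earlier scans and angiogram-only subjects have no consistent rule

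*Combined protocol and SAP*

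**What the plan says.** Section 16.9 (Primary Statistical Analysis) admits a subject to the patency denominator by one of three routes:

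- a "core-lab adjudicated DUS ultrasound finding of either patent or not patent at 12 months";
- a CD-TLR before the 12-month window closes, which counts as a failure;
- "missing 12 month DUS with a patent DUS finding at a subsequent visit with no intervening clinically driven TLR", which counts as a success.

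The same paragraph has a separate angiogram rule. It begins "In the event an angiogram is available within the 12 month visit window" and lets the angiographic core lab's reading, at a 50% stenosis cutoff, replace the DUS reading.

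Section 16.6 describes the primary analysis as observed data with "standard imputations used when the 12 month DUS determination is missing but an earlier or later DUS" or angiogram is available. For detail it points to Section 16.8, which in the current numbering is the safety objective. Section 16.6 also specifies best-case, worst-case and tipping-point sensitivity analyses.

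On when scans happen, Section 12.6 states: "The DUS exam should be performed on all subjects at the 30-day, 6, and 12 month follow-up visits". Table 5 schedules none later. Its footnote on non-diagnostic scans says "the site should make every effort to obtain a repeat exam within the visit window", and its footnote on unscheduled imaging reads "If clinically indicated or per standard of care". Section 12.8 defines an unscheduled visit as one "for a target limb related adverse event or intervention to target limb".

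**The concern.** The first route takes a scan whichever way it reads. The third takes only one reading. Two subjects can have the same history (no 12-month DUS, one later DUS, no CD-TLR) and be treated differently purely because of the result: the patent one adds a success, and the other disappears. This happens inside the test that decides the trial.

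Because no DUS is scheduled after 12 months, a later one is either a late repeat of a missed or non-diagnostic 12-month scan or an unscheduled scan done for clinical reasons. The second kind may well be enriched for restenosis, which is the reading the rule discards.

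Two gaps sit beside this. A subject with only an in-window angiogram and no CD-TLR has a rule for reading the image but no listed place in the denominator. A subject whose last DUS was at 30 days or 6 months is covered by the imputation announced in 16.6, yet has no rule in 16.9. Both leave room to settle the denominator after results are known.

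**Working it through.** **Inputs from the plan (Section 16.9):** exact one-sample test, one-sided alpha 0.025, performance goal 53% (60% drug-coated balloon), assumed patency 65%, 178 evaluable subjects.

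**Assumptions:** F, the number of subjects with no 12-month DUS but a later DUS, is not given; I take 1 to 8 and expect the low end. Unless stated otherwise, 178 subjects have a 12-month DUS and missingness is unrelated to outcome.

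**Step 1. Reproduce the plan.** The smallest r with P(X ≥ r | 178, 0.53) ≤ 0.025 is 108. Actual size is 0.0237 and power at 65% is 0.900. This matches the stated 90.0%, so the sample size is not in question.

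**Step 2. False-success rate.** Let X ~ Bin(178, 0.53) and Y ~ Bin(F, 0.53). As written, the test sees X + Y successes out of 178 + Y. A symmetric rule sees X + Y out of 178 + F. The exact cutoff is recalculated for each denominator. The last two columns average over 168 to 188 subjects with a 12-month DUS, to smooth the steps of the exact test.

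| F | As written | Symmetric | As written, averaged | Symmetric, averaged |
|---|---|---|---|---|
| 1 | 0.0237 | 0.0202 | 0.0229 | 0.0210 |
| 2 | 0.0264 | 0.0248 | 0.0249 | 0.0210 |
| 3 | 0.0290 | 0.0213 | 0.0270 | 0.0210 |
| 8 | 0.0397 | 0.0200 | 0.0402 | 0.0212 |

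On the averaged figures, each later-DUS subject adds about 0.2 percentage points. If the 178 already includes the F subjects, the as-written rates are 0.0237, 0.0252, 0.0271 and 0.0389, against 0.0237 under a symmetric rule.

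**Step 3. Overstatement of patency.** The expected estimate as written is about (178p + Fp)/(178 + Fp). With p = 0.53 and F = 3 this is (94.34 + 1.59)/(178 + 1.59) = 95.93/179.59 = 53.42%, or 0.42 points too high. For F = 1, 2, 3 and 8 the overstatement is 0.14, 0.28, 0.42 and 1.09 points. At p = 0.65 it is 0.13, 0.25, 0.38 and 0.99 points.

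**Step 4. Symptom-driven later scans.** Suppose only 30% of later scans are patent (an assumption). As written the expected rate is (94.34 + 0.3F)/(178 + 0.3F); counting everyone it is (94.34 + 0.3F)/(178 + F). For F = 8 these are 96.74/180.4 = 53.6% and 96.74/186 = 52.0%. The overstatement for F = 1, 2, 3 and 8 is 0.21, 0.41, 0.62 and 1.61 points. The false-success rate is 0.0237, 0.0245, 0.0258 and 0.0318.

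**Step 5. A borderline result.** If two of 178 subjects have a later, not-patent DUS and both are counted, 107/178 gives one-sided p = 0.0335 and the trial fails. Dropping those two gives 107/176, p = 0.0225, and it passes.

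**Step 6. Angiogram and earlier DUS.** No arithmetic applies, because the documents give no counts. Section 16.6 names earlier DUS, later DUS and angiogram as sources; the 16.9 denominator contains only the later DUS, and only when patent.

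**The case against.** The best case for the plan has four parts.

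*The route is nearly empty.* With scans only to 12 months, a ±30-day window and repeats sought inside it, F should be low. At F = 1 the false-success rate stays under 2.5%, and at F = 2 the averaged rate is about 2.5%. This stands, and it is why the effect is called small.

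*Another route pulls the other way.* CD-TLR subjects enter as failures without a DUS, while other subjects without one are dropped. If one such failure would otherwise have had no DUS (also an assumption), the rates for F = 1, 2 and 3 become 2.0%, 2.2% and 2.3%; at F = 8 the rate is still 3.3%. This stands as a limit on the claim: the Step 2 rates describe one route, not the whole test. It does not justify selecting on the reading.

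*The rule has clinical logic.* Patency later supports patency at 12 months, whereas restenosis later may have begun after 12 months. That is a fair reason for each classification taken alone. It is not a reason to let a subject into the denominator only when the answer is favorable. It does weigh in favor of using no later DUS.

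*The gaps are drafting, and 16.6 exposes the dropped subjects.* The 16.9 list can be read as closed, which would drop subjects whose last DUS was at 6 months whether patent or not. But 16.6 says otherwise, so the sections conflict. Worst-case and tipping-point analyses do show the effect of the dropped subjects, but they leave the primary test unchanged, and the best case scores a later not-patent subject as a success.

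**Conclusion.** The concern holds. One route into the primary analysis selects on the outcome and pushes patency upward, and the denominator is not consistently defined for angiogram-only and earlier-DUS subjects. The size is small: roughly 0.14 points of patency per later-DUS subject at 53%, and a false-success rate that clearly passes 2.5% only from about F = 3. These figures rest on the assumed F, on 178 subjects with a 12-month DUS and, except in Step 4, on missingness unrelated to outcome. No net bias over all routes is claimed, and no figure is claimed for angiogram-only subjects. It should be fixed because it is a definite defect in the primary endpoint definition and a handful of subjects could decide a borderline result.

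**What to change.** In Section 16.9:

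1. If the 12-month DUS is missing, use the first core-lab DUS after the window whichever way it reads, up to a stated latest day; or use no later DUS at all. Either choice is independent of the result.
2. Add subjects with only an in-window core-lab angiogram to the denominator, as patent or not patent.
3. Reconcile 16.6 with 16.9 on earlier DUS, and point the cross-reference in 16.6 to 16.9.

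Optionally, prespecify a sensitivity analysis that scores core-lab restenosis at 30 days or 6 months with no 12-month DUS as failure, and bar the best case from scoring it as success. Do not carry only the earlier failures into the primary analysis. That is one-sided downward: adding 3, 6 or 10 such failures to the 178 cuts power at 65% from 0.900 to 0.835, 0.747 or 0.638.

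The cost is SAP wording. The images are already collected and read by the core labs. The downside is a slightly lower patency estimate, or the loss of the F subjects if no later DUS is used.
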